#### **9.14.2 Clinical Laboratory Results**

Laboratory parameters will be summarized (e.g., total bilirubin, serum creatinine). Descriptive statistics (n, mean, standard deviation, median, minimum, and maximum) as well as changes from baseline (i.e., within 24 hours before conditioning begins for the DP arm and on the day conditioning begins for the BSC arm) will be summarized by study phase and treatment received during the Prophylaxis Phase. The number and percentage of patients with abnormal values postbaseline and other summary statistics (i.e., mean, minimum, maximum, standard deviation, and number of patients) will be presented by study phase and treatment received during the Prophylaxis Phase for each laboratory parameter as per protocol schedule.

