5 CHANGES IN THE CONDUCT OF PLANNED ANALYSES

Three TEAEs of special interest (pulmonary hemorrhage, gastrointestinal bleeding, and hypersensitivity reactions) will be summarized. This is not specified in the protocol.

Section 10.1 clarifies censoring rules for subjects who don't undergo HSCT. The protocol defines the timing variable for these subjects but does not describe how these subjects who are not at risk of post-HSCT events should be censored.

Section 10.1 also added censoring rules for subjects who develop VOD prior to HSCT. This scenario is a possible outcome, albeit rare, and was not addressed in the protocol.

Section 8.2.1 clarifies how baseline is defined. The protocol defines baseline as follows: "Baseline/Study Day 1 is defined as the day before conditioning begins for patients randomized to the DP arm and the day that conditioning begins for patients randomized to the BSC arm." As the first dose of defibrotide is administered within 24 hours prior to the first dose of conditioning for subjects randomized to DP arm, the two definitions should result into the same Study Day 1 if the subjects strictly follow the protocol. In practice, it is possible that the subjects receive the first dose of defibrotide and then do not start conditioning on the next day. Thus, the definition in the protocol could result in a baseline assessment that occurs after defibrotide administration begins. For safety analyses, the baseline value should be the last assessment taken prior to study drug administration. For this reason, the definitions of Baseline/ Study Day 1 and of baseline values were further clarified in the SAP and this is the default definition used in the analyses.

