8.2 Baseline and Study Day Definitions

8.2.1 Baseline Date (Study Day 1)

Baseline is defined as the earliest date of the first dose of defibrotide or conditioning therapy.

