8.2.2 Baseline Value

For assessments where time was collected for both the assessment and the first dose, the baseline value is defined as the last nonmissing value collected on or before the time of the first dose. For assessments where time was not collected, the baseline value is defined as the last nonmissing value collected on or before the date of the first dose. For subjects who do not have at least one dose of defibrotide or conditioning therapy, the baseline value is defined as the value that was collected where nominal Visit = Baseline. If this value is missing, then baseline value is defined as the value collected where Visit = Screening.

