8.3 Study Phase

In this study, the occurrence of VOD and the administration of rescue defibrotide represent a clinical landmark time point for safety. Therefore, for the safety analyses, 2 study phases are defined with respect to the administration of rescue defibrotide, as follows:

- **Prophylaxis Phase:**
 - If VOD occurs, the prophylaxis phase starts on the Baseline date and ends on the day before the start date of rescue defibrotide (ie, rescue treatment start date – 1).
 - If VOD does not occur, the prophylaxis phase starts on the Baseline date and ends on the date of study completion/early termination.
- **Rescue Treatment Phase:**
 - For the subset of subjects who developed VOD and received rescue defibrotide, the rescue treatment phase begins on the start date of rescue defibrotide and ends on the date of study completion/early termination.

The start date of rescue defibrotide will be derived as the date of the first administration of defibrotide on or after the investigator diagnosis of VOD.

Unless otherwise noted, safety summaries will be reported by study phase and by treatment received during the Prophylaxis Phase.

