8.4.1 Laboratory Parameters

For the laboratory (hematology, coagulation and chemistry) parameters, Table 1 below provides the analysis windows for the purpose of identifying the assessments to be used in the analyses during the prophylaxis phase. Table 2 provides the analysis windows for the rescue phase.

Table 1 - Analysis Window for Laboratory Parameters During Prophylaxis Phase

Visit Identifier	Nominal Day	Lower Limit: HSCTSTDY	Upper Limit: HSCTSTDY
Baseline		The last nonmissing value collected on or before the first dose.	
Day +1 post-HSCT	HSCTSTDY=2	1	4
Day +7 post-HSCT	HSCTSTDY=8	5	11
Day +14 post-HSCT	HSCTSTDY=15	12	18
Day +21 post-HSCT	HSCTSTDY=22	19	25
Day +30 post-HSCT	HSCTSTDY=31	26	34
Day +37 post-HSCT	HSCTSTDY=38	35	41
Day +44 post-HSCT	HSCTSTDY=45	42	48
Day +51 post-HSCT	HSCTSTDY=52	49	55
Day +60 post-HSCT	HSCTSTDY=61	56	66
Day +100 post-HSCT	HSCTSTDY=101	96	106
Day +180 post-HSCT	HSCTSTDY=181	171	191

HSCTSTDY = DATE – (Date of Day +0 post-HSCT) + 1, where DATE is the date of the lab assessment.

Table 2 - Analysis Window for Laboratory Parameters During Rescue Phase

Visit Identifier	Nominal Day	Lower Limit: HSCTSTDY	Upper Limit: HSCTSTDY
Baseline		The last nonmissing value collected on or before the first dose.	
Day +1 post-VOD Treatment	HSCTSTDY=2	1	4
Day +7 post-VOD Treatment	HSCTSTDY=8	5	11

Day +14 post-VOD Treatment	HSCTSTDY=15	12	18
Day +21 post-VOD Treatment	HSCTSTDY=22	19	25
Day +30 post-VOD Treatment	HSCTSTDY=31	26	34
Day +37 post-VOD Treatment	HSCTSTDY=38	35	41
Day +44 post-VOD Treatment	HSCTSTDY=45	42	48
Day +51 post-VOD Treatment	HSCTSTDY=52	49	55
Day +60 post-VOD Treatment	HSCTSTDY=61	56	64
Day +67 post-VOD Treatment	HSCTSTDY=68	65	71
Day +30 post-HSCT ^a	HSCTSTDY=31	26	34
Day +100 post-HSCT ^a	HSCTSTDY=101	96	106
Day +180 post-HSCT ^a	HSCTSTDY=181	171	191

HSCTSTDY = DATE – (Date of Day +0 post-VOD Treatment) + 1, where DATE is the date of the lab assessment.

^a HSCTSTDY = DATE – (Date of Day +0 post-HSCT) + 1, where DATE is the date of the lab assessment. If Day +30, +100 or +180 post-HSCT visit occurs during the Rescue Phase, the corresponding records will be summarized twice (once at post-VOD Treatment summary and once at post-HSCT summary).

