11.3 Laboratory Assessments

For all hematology, coagulation, and chemistry parameters, the lab values at baseline and each of the postbaseline assessments will be summarized and presented using descriptive statistics. See Section [8.4.1](#) for the identification of the assessments used in the analyses. For each of the postbaseline assessments, change between baseline and that assessment in a specific lab value will be calculated as follows,

Change from baseline = [Lab value at the post-baseline assessment] – [Lab value at baseline],

and will be summarized and presented using descriptive statistics. If the lab value is missing at either baseline or a specific post-baseline assessment for a subject, change from baseline will be missing.

- Summary of clinical laboratory results: Hematology
- Summary of clinical laboratory results: Chemistry
- Summary of clinical laboratory results: Coagulation

For each of the following select laboratory parameters: total bilirubin, serum creatinine, absolute neutrophil count, and platelet count, a shift table from baseline grade to the highest postbaseline grade will be provided:

- Shift table of selected postbaseline laboratory results from baseline

All laboratory results will be listed. In addition, a listing of subjects who have abnormal postbaseline lab values for select lab parameters (total bilirubin, serum creatinine, absolute neutrophil count, and platelet count) will be provided with corresponding normal ranges. The following listings will be provided:

- Listing of clinical laboratory results: Hematology
- Listing of clinical laboratory results: Chemistry
- Listing of clinical laboratory results: Coagulation

- Listing of subjects with abnormal post-baseline laboratory values

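### The Rescue Phase has no baseline of its own, so changes on rescue defibrotide are measured from before conditioning

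*SAP*

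**What the plan says.** SAP 8.2.1: "Baseline is defined as the earliest date of the first dose of defibrotide or conditioning therapy". SAP 8.2.2 adds that, where times exist, "the baseline value is defined as the last nonmissing value collected on or before the time of the first dose". SAP Section 5 explains why the definition was clarified and says that "this is the default definition used in the analyses". The same paragraph states the principle behind it: for safety, baseline should be the last assessment before study drug is given.

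SAP 8.3 splits safety into two phases because VOD and rescue are a landmark for safety. For rescued patients "the rescue treatment phase begins on the start date of rescue defibrotide and ends on the date of study completion/early termination". The start date is the first defibrotide administration on or after the investigator's diagnosis. The day before it closes the Prophylaxis Phase.

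Table 2 in SAP 8.4.1 gives the Rescue Phase windows. Its baseline row, "The last nonmissing value collected on or before the first dose", is identical to the row in Table 1 for the Prophylaxis Phase. Days are counted as "HSCTSTDY = DATE – (Date of Day +0 post-VOD Treatment) + 1". SAP 8.4.3 applies Table 2 to vital signs other than the intensive infusion readings.

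SAP 11.3 summarises values and changes from baseline at each visit. For bilirubin, creatinine, neutrophils and platelets, "a shift table from baseline grade to the highest postbaseline grade will be provided". SAP 11.4 summarises the maximum blood-pressure decrease from baseline in order to look for hypotension around infusions. Protocol 9.14.2 asks for laboratory change by study phase from a baseline taken "within 24 hours before conditioning begins for the DP arm and on the day conditioning begins for the BSC arm".

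**The concern.** A phase split is useful if each phase can be read against the patient's state on entering it. Here the Rescue Phase inherits a reference value from before conditioning, transplant and VOD. Every Rescue Phase change then includes whatever happened in that interval, and a reader cannot separate it from what happened on rescue. Bilirubin above 2 mg/dL is one of the VOD criteria (protocol 6.3.1.1), so raised values at rescue entry are to be expected.

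The principle in SAP Section 5 sharpens the point for rescued BSC patients. Their first defibrotide is the rescue dose, so the last assessment before study drug is the pre-rescue value, not the pre-conditioning one. The blood-pressure summary has the same difficulty: a maximum decrease meant to detect an infusion effect would be measured, in the Rescue Phase, from a reading taken before conditioning.

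A second, smaller issue is the opening day. The phase starts on a calendar date, and the SAP has no rule separating pre-dose from post-dose laboratory values on that date.

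**Working it through.** **1. Which dose is meant.** The Table 2 row does not qualify its first dose. SAP 8.2.1 ties baseline to the first defibrotide or conditioning dose, SAP 8.2.2 treats patients with neither as the exception, and protocol 9.14.2 anchors laboratory change to the start of conditioning. Together these point to the pre-conditioning value. A programmer could still read Table 2 as the first rescue dose, which would produce different tables.

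**2. Day count.** The Table 2 formula gives HSCTSTDY = X + 1 for Day +X after rescue start. This reproduces all ten post-VOD rows: Days +1, 7, 14, 21, 30, 37, 44, 51, 60 and 67 give 2, 8, 15, 22, 31, 38, 45, 52, 61 and 68. The rescue start date is 0 + 1 = 1, inside the Day +1 window of 1 to 4. The day before is −1 + 1 = 0, outside the window and in the Prophylaxis Phase.

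**3. Whether the start-day value reaches the Day +1 summary.** SAP 8.4 takes the date closest to the nominal day (here 2), and ties go to the later date.

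| Days with a value | Day selected |
|---|---|
| 1, 2 (with or without 3, 4) | 2 |
| 1, 3 (with or without 4) | 3 (tie, later date) |
| 1, 4 | 1 |
| 1 only | 1 |

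Day 1 is selected only if days 2 and 3 are both missing. Bilirubin is measured daily in hospital (protocol 7.4.1.2), so day 2 is used. The protocol lets other chemistry and hematology fall to three times weekly. On a Monday/Wednesday/Friday schedule, a Monday or Wednesday start selects day 3 and only a Friday start selects day 1. Coagulation may be weekly, so it is the most exposed.

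**4. The shift table.** It takes the highest post-baseline grade and has no closest-day rule. A start-day sample drawn before the first rescue dose is therefore eligible to set the highest Rescue Phase grade.

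**5. Effect on the change.** For pre-conditioning value b, pre-rescue value r and on-rescue value v, the tabulated change is v − b and the change on rescue is v − r. They differ by r − b at every visit. They have opposite signs when v lies strictly between b and r. The values below are assumed for illustration (bilirubin, mg/dL, r = 5.0).

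| Day | v | v − b, b = 0.6 | v − r |
|---|---|---|---|
| +1 | 4.5 | +3.9 | −0.5 |
| +7 | 2.5 | +1.9 | −2.5 |
| +14 | 1.2 | +0.6 | −3.8 |
| +21 | 0.6 | 0.0 | −4.4 |

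The constant gap is 5.0 − 0.6 = 4.4. With b = 1.8 and values 4.5, 2.5, 1.2 and 0.8, the tabulated changes are +2.7, +0.7, −0.6 and −1.0, against −0.5, −2.5, −3.8 and −4.2 from r; the gap is 3.2. The sign disagrees only until the value is back to its pre-conditioning level.

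In both cases a pre-dose 5.0 on the start date would be the highest listed Rescue Phase value, against 4.5 if it were assigned to baseline. Whether that alters a grade depends on grading limits that the documents do not give.

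**The case against.** The strongest defence is that the protocol chose this baseline. Protocol 9.14.2 asks for change from the start of conditioning by study phase, and the SAP follows it. The SAP also treats conditioning as study treatment when it defines treatment-emergent events, so the principle in Section 5 can be read as satisfied. This stands as a reason to keep the existing change. It does not supply a change since rescue start.

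Second, actual values are summarised at every visit and VOD resolution is analysed on its own criteria (SAP 10.2.2.5), so a fall is visible. Even the tabulated +3.9, +1.9, +0.6, 0.0 shows improvement. A reader might infer that recovery as such is reported as deterioration. The documents do not support that: full return to baseline shows as zero, and a positive change correctly says that the value is still worse than before conditioning.

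Third, a reader might infer that the diagnosis-day value counts as on-rescue. The phase and the day count begin at rescue start. If rescue starts on a later date than diagnosis, the diagnosis-day value stays in the Prophylaxis Phase. The two dates are likely to coincide for DP patients still being dosed, because the next administration sets the start date.

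Fourth, a pre-rescue baseline has its own weakness. It selects many patients near a peak, so regression to the mean and ordinary post-transplant recovery would look like benefit in a phase without a control. This stands and governs how the new tables should be labelled.

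**Conclusion.** The point holds in a limited form and is a low-cost improvement. Rescue Phase laboratory and vital-sign changes, the laboratory shift table and the maximum blood-pressure decrease are referenced to before conditioning, and nothing reports change since rescue start. Per patient the discrepancy is the pre-rescue value minus the pre-conditioning value: 4.4 and 3.2 mg/dL in the two assumed bilirubin cases. The documents give no rescue-entry values, so the size in this trial cannot be stated. For rescued BSC patients the choice also departs from the SAP's stated safety principle, if study drug there means defibrotide, as in protocol 5.1.1.

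The start-day issue matters mainly for the shift table and for sparsely sampled tests.

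Three wider readings should not be drawn. Adverse-event counts do not use this baseline. The tables are descriptive and do not attribute conditioning or VOD toxicity to rescue. Performance scores have their own row at rescue start in Table 3, and their written change formula in SAP 11.7 subtracts assessment dates rather than scores; that is a separate error needing its own correction. Vital signs in general have no single worse direction, so for them the sign argument is confined to the blood-pressure decrease.

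**What to change.** - In Table 2, state which first dose the baseline row means.
- In SAP 8.2.2, add a Rescue Phase baseline: the last value before the first rescue dose by date and time, or on or before that date if no time was collected. Allow it to come from the Prophylaxis Phase.
- Assign start-day pre-dose values to that baseline, and count only later values as on-rescue.
- Present Rescue Phase laboratory and vital-sign changes, shifts and maximum blood-pressure change from it, alongside the change from study baseline in protocol 9.14.2. Do not replace the latter or reduce it to a listing.
- Label the added tables descriptive, with a note on regression to the mean and natural recovery, and record the addition in SAP Section 5.

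The cost is SAP wording, one baseline flag and a second set of descriptive tables. No new sampling is needed, but the visit at VOD diagnosis does not itself list laboratory tests (protocol 7.4.1.1). The pre-rescue value must come from the routine schedule, and for coagulation it may be several days old.

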8.4.2 Karnofsky and Lansky Performance Scores

For the Karnofsky and Lansky performance scores, Table 3 provides the analysis windows for the purpose of identifying the assessments to be used in the analyses.

Table 3 - Analysis Window for Karnofsky and Lansky Performance Scores

Visit Identifier	Nominal Day	Lower Limit: HSCTSTDY	Upper Limit: HSCTSTDY
Baseline		The last nonmissing value collected on or before the first dose.	
Day +0 post-VOD Treatment ^a	HSCTSTDY=1	1	4
Day +1 post-HSCT	HSCTSTDY=2	2	5
Day +7 post-HSCT	HSCTSTDY=8	6	12

Day +15 post-HSCT	HSCTSTDY=15	13	25
Day +30 post-HSCT	HSCTSTDY=31	26	51
Day +60 post-HSCT	HSCTSTDY=61	52	81
Day +100 post-HSCT	HSCTSTDY=101	82	141
Day +180 post-HSCT	HSCTSTDY=181	142	191

HSCTSTDY = DATE – (Date of Day +0 post-HSCT) + 1, where DATE is the date of the lab assessment.

^a Rescue Phase only. HSCTSTDY = DATE – (Date of Day +0 post-VOD Treatment) + 1, where DATE is the date of the lab assessment.

8.4.3 Vital Signs

Intensive vital signs recorded during the first and second infusion of defibrotide on the first day of defibrotide dosing will be summarized at the nominal visit and time recorded in EDC. The analysis windows for all other visits will follow Table 1 and Table 2 in [Section 8.4.1](#) for the prophylaxis and rescue phases, respectively.

9 STUDY POPULATION SUMMARIES

9.1 Enrollment

The number of subjects in each analysis set will be tabulated overall and by treatment group with the exception of screened subjects, who will only be tabulated in the Total column. The ITT Analysis Set will be further summarized by randomization strata. Counts and percentages will be presented for each stratification level separately (High Risk, Very High Risk, Adult, and Pediatric) and for the 4 combinations of strata for risk status and age group across all countries and centers and separately by center within country.

Additionally, summaries for public disclosure will tabulate subjects enrolled by country and site and by age category in the ITT Analysis Set.

The following summaries will be provided:

- Summary of analysis sets
- Summary of randomized subjects by risk status, age group, country, and center within country
- Number of subjects enrolled by country and site (for public disclosure)
- Number of subjects enrolled by age category (for public disclosure)

The following listings will be provided:

- Listing of analysis sets
 - This listing will include a column header for each Analysis Set. Subjects will be flagged as “Yes” or “No” depending on whether or not they are included in each Analysis Set.

- Listing of informed consent and eligibility
 - This listing will include the date of informed consent/assent, the protocol version for consent/assent, and inclusion and exclusion criteria that were not met for all enrolled subjects.
- Stratification at randomization
 - This listing will include each stratification factor of risk status, age group, and country collected in IRT at randomization.
- Discrepancies in risk status between IRT and EDC
 - This listing will include subjects who had a discrepant risk status between EDC and IRT. Stratification at randomization was based on data entered in IRT at the time of randomization. If this status was later found to be incorrect it was not changed in IRT but the correct status was entered into EDC.
- Reasons for Screen Failure
 - This listing will include the previous screening number (if applicable), screening date, and reason for screen failure for all subjects who failed screening and were not randomized.

9.2 Disposition

9.2.1 Subject Disposition

A summary and listing of subject disposition, including study completion, study withdrawal, and reasons for study withdrawal, will be provided overall and by treatment group. Additionally, a disposition summary by study period for public disclosure will be provided in the ITT Analysis Set.

The following summaries will be provided:

- Summary of subject disposition
- Study disposition by study period (for public disclosure)

The following listing will be provided:

- Subject disposition

9.2.2 Study Treatment Disposition during Prophylaxis Phase

A summary and listing of DP disposition including the number of subjects who received at least one dose of DP treatment, DP completion, DP discontinuation, and reasons for DP discontinuation will be provided for the DP arm using the ITT Analysis Set.

The following summaries will be provided:

- Summary of DP treatment disposition

The following listing will be provided:

- Listing of DP treatment disposition

9.2.3 Study Treatment Disposition during Rescue Phase

A summary and listing of defibrotide rescue treatment disposition including the number of subjects who received at least one dose of defibrotide rescue treatment, defibrotide rescue treatment completion, defibrotide rescue treatment discontinuation, and reasons for defibrotide rescue treatment discontinuation will be provided overall and by treatment group using the ITT Analysis Set.

The following summaries will be provided:

- Summary of defibrotide rescue treatment disposition

The following listing will be provided:

- Listing of defibrotide rescue treatment disposition

9.3 Protocol Deviations

Protocol deviations are classified as major or minor in accordance with the Protocol Deviation Management Plan. Major protocol deviations will be summarized overall and by treatment group for the ITT Analysis Set. Subjects with more than one major protocol deviations will be counted only once in the total number of subjects with major protocol deviations.

The following summaries will be provided:

- Summary of major protocol deviations

The following listing of all protocol deviations will be provided:

- Listing of all protocol deviations
 - This listing will include deviation type, deviation category, date of deviation, a description, and whether it was major or minor.

